Specific Aim 2: Determine the extent to which retention of performance is associated with individual differences in baseline and practice-induced changes in brain measures (working memory, gray matter volume, task-based prefrontal activity, and brain network segregation).

Specific Aim 3: Investigate the extent to which tDCS modifies resting state network segregation. We anticipate that prefrontal tDCS will augment retention of locomotor learning, and that our data will provide the first evidence of specific brain mechanisms responsible for locomotor learning/retention in older adults. This new knowledge will provide a clinically feasible intervention approach as well as reveal mechanistic targets for future interventions to enhance locomotor learning and rehabilitation.

4. Background:

Aging often leads to substantial declines in walking function, especially for walking tasks that are more complex such as obstacle crossing. This is due in part to a lack of continued practice of complex walking (sedentary lifestyle) combined with age-related deficits of brain structure and the integrity of brain networks. Neurorehabilitation can contribute to recovery of lost walking function in older adults, but major and persistent improvements are elusive. A cornerstone of neurorehabilitation is motor learning, defined as an enduring change in the ability to perform a motor task due to practice or experience. Unfortunately, in most clinical settings, the time and cost demands of delivering a sufficiently intensive motor learning intervention is not feasible. There is a need for research to develop strategies for enhancing motor learning of walking ("locomotor learning") in order to improve the effectiveness of neurorehabilitation.

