The objective of this study is to use non-invasive brain stimulation to augment locomotor learning and to investigate brain networks that are responsible for locomotor learning in older adult Veterans. We have shown that frontal brain regions, particularly prefrontal cortex, are crucial to control of complex walking tasks. Our neuroimaging and neuromodulation studies also show that prefrontal cortex structure and network connectivity are important for acquisition and consolidation of new motor skills. For instance, our published data shows that resting state connectivity of prefrontal networks predicts sensorimotor task performance and learning. Furthermore, prefrontal tDCS enhances multi-day retention of performance on a complex dart throwing task. However, a major gap exists regarding learning of locomotor (walking) tasks. This study is designed to address this gap. Our pilot data show that bihemispheric prefrontal tDCS administered during a single session of learning on a complex obstacle walking task contributes to multi-day retention of task performance. In this study we will build upon this pilot work by conducting a full-scale trial that also investigates mechanisms related to brain structure, functional activity, and network connectivity.

5. Specific Aims:

Specific Aim 1: Determine the extent to which prefrontal tDCS augments the effect of task practice for retention of performance on a complex obstacle walking task.

Hypothesis 1: Retention on the obstacle walking task at 1-week (primary outcome) and 1-month post-training will be significantly higher for an active prefrontal tDCS group versus a sham tDCS group.

Specific Aim 2: Determine the extent to which retention of performance is associated with individual differences in baseline and practice-induced changes in brain measures.

Hypothesis 2a: Better retention on the obstacle walking task will be associated with baseline greater working memory performance, greater prefrontal gray matter volume, and greater task-based prefrontal fNIRS activity.

Hypothesis 2b: Better retention on the obstacle walking task will be associated with training-induced increased prefrontal gray matter volume and reduction of task-based prefrontal fNIRS activity (indicating neural efficiency and/or reduced executive demands).

Hypothesis 2c: Better retention on the obstacle walking task will be associated with baseline network connectivity, including resting default mode network segregation.

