For Specific Aim 1 we seek to determine whether active tDCS is superior to sham tDCS for enhancing retention of locomotor learning after one week. The primary outcome is the change in walking speed on the obstacle course between the end of the learning period to the one week post visit. We are powering the study to detect group differences in retention of walking performance. We will use an ANOVA model to test group differences, and will account for demographic covariates. To estimate sample size for this aim, we have conducted a pilot study with 12 older adult participants who were randomized to an active (n=5) or sham (n=7) tDCS group. To assess retention, the mean walking speed from the final three trials of the learning session were compared to the mean walking speed from the three retention trials measured one week later. The active tDCS group showed a between-session gain in walking speed of nearly 0.07 m/s. The sham tDCS group showed a drop in between-session speed of approximately -0.04 m/s. This between group-difference of 0.1 m/s is considered clinically meaningful and had a large effect size of 0.87. The whole-group standard deviation of response was 0.12. Based on these preliminary data, we will need 48 participants (n=24 per group) to detect a statistically significant group difference at alpha=0.05 and beta=0.20 (i.e., 80% power). To be conservative, we will enroll 60 participants to account for potential dropout and to ensure sufficient statistical power.

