For Specific Aim 2 we seek to determine if several key measures of brain integrity/function help to explain individual differences in the retention of locomotor learning after one week. We will use multivariate regression models that account for demographic covariates. Based on the assumptions of univariate linear regression, a sample size of 60 with alpha=0.05 and beta=0.20 (i.e., 80% power) will allow us to significantly detect correlations coefficients as small as 0.355. Values below this level are generally considered very weak, and thus there would be little benefit to powering the study to detect smaller values. Based on our pilot data and findings from the literature, we are very likely to observe stronger associations that will achieve statistical significance. For instance, our pilot data show that working memory performance and prefrontal activation are associated with visuomotor learning with correlations of 0.57 and 0.48, respectively. Our pilot data also show that resting state default mode network connectivity is associated with retention of learning with a correlation of 0.46. Our statistical models will account for a number of demographic and other covariates, thereby accounting for some of the variability in the data set and improving our ability to detect these mechanism-related associations.

For Specific Aim 3 we seek to acquire evidence that tDCS modifies resting state network connectivity and segregation during motor learning. Prior studies have shown that even a single session of motor learning or a single session of tDCS can modify the connectivity of resting state brain networks. However, this remains an exploratory aim and we have not specifically powered the study for this purpose. Nevertheless, as with the other measures described above, if the effect size is moderate or large we are likely to detect it with statistical significance.

Data and Safety Monitoring Plan

Adverse Event Reporting

Adverse events will be reported according to the guidelines of the University of Florida Institutional Review.

Reporting within 5 days of the PI becoming aware will apply to adverse events that meet all of the following criteria:

- Serious
- Unexpected
- Related or the Relationship is “more likely than not”

Adverse events will be added to the cumulative event table and reported at continuing review when they meet either of the following criteria:

- Serious (but expected) and related or the relationship is “more likely than not”.

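### Aim 2 regressions do not name randomised arm: this may forgo precision for baseline predictors and leaves the target association undefined for change predictors

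*Combined protocol and SAP*

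**What the plan says.** Section 10 gives the Aim 2 analysis in one sentence: "We will use multivariate regression models that account for demographic covariates". The same paragraph ends by promising that "Our statistical models will account for a number of demographic and other covariates", and gives the purpose as "thereby accounting for some of the variability in the data set and improving our ability to detect these mechanism-related associations". The other covariates are not listed. No section names randomised arm, stratification by arm or an arm-by-predictor term for Aim 2.

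The power statement is made "Based on the assumptions of univariate linear regression", with a sample size of 60, alpha 0.05, 80% power and a smallest detectable correlation of 0.355. Sixty is the total enrolment given for Aim 1 in the same section, so both arms are pooled. That is an inference; the text does not say it in words.

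The outcome is one-week retention, which Aim 1 also uses. Hypothesis 1 (section 5) expects that retention "will be significantly higher for an active prefrontal tDCS group versus a sham tDCS group". Section 10 reports a pilot difference that "is considered clinically meaningful and had a large effect size of 0.87".

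The predictors are of two kinds. Hypotheses 2a and 2c use baseline measures. Hypothesis 2b says better retention will be "associated with training-induced increased prefrontal gray matter volume and reduction of task-based prefrontal fNIRS activity", which is change measured after stimulation. The abstract's wording of Aim 2 is wider: "baseline and practice-induced changes in brain measures (working memory, gray matter volume, task-based prefrontal activity, and brain network segregation". Read literally, it also covers change in segregation. Hypothesis 3 predicts a tDCS effect on segregation, and section 10 calls that aim exploratory.

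**The concern.** By the protocol's own expectation, arm is a strong determinant of the Aim 2 outcome, yet it is not among the named covariates. What that means depends on the predictor.

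- **Baseline predictors (2a, 2c).** Randomisation makes these independent of arm, so omitting arm does not bias the slope. It leaves any tDCS effect on retention in the residual. That works against the plan's stated reason for using covariates.
- **Change predictors (2b, and segregation change if it is analysed as the abstract lists it).** Stimulation is delivered during practice, so these measures could themselves be shifted by tDCS. If so, the pooled slope combines a within-arm part (people who change more retain more) with a between-arm part (tDCS moved both variables). Aim 2 is about individual differences, and a model without arm cannot separate the two. A shift against the hypothesised direction could also hide a real within-arm association.

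The text does not say which association is the target. Either can be valid, but they answer different questions.

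**Working it through.** **1. The plan's own figure.** Fisher z, two-sided 5%, 80% power, N=60: r = tanh((1.960 + 0.842)/√57) = tanh(2.802/7.550) = 0.355. The stated value reproduces. It is a marginal correlation with no covariates.

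**2. Baseline predictors.** Inputs: marginal r=0.355, n=60, 1:1 arms, unit within-arm SD. Retention d is 0.87 (pilot, section 10), half of it (0.435, assumed) or 0. Arm explains (d²/4)/(1+d²/4) of the outcome variance, which is 0.159 at d=0.87 and 0.045 at 0.435. The within-arm correlation is 0.355·√(1+d²/4). Power is from simulation of the slope t-test, 200,000 replicates per cell.

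| Retention d | Within-arm r | Power without arm | Power with arm |
|---|---|---|---|
| 0.87 | 0.387 | about 80% | 87% |
| 0.435 | 0.363 | about 80% | 82% |
| 0 | 0.355 | about 80% | under 1 point lower |

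The Fisher approximation agrees: with arm at d=0.87, Φ(atanh(0.387)·√56 − 1.960) = 0.86. Taking 0.10 m/s over a within-arm SD of 0.12 (d=0.83) instead of 0.87 also gives 86%.

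**3. Change predictors, no within-arm association.** The tDCS effect on the brain measure is not in the documents; d=0 to 0.5 is assumed. If both variables shift in the same direction, the pooled correlation is (d₁d₂/4)/√((1+d₁²/4)(1+d₂²/4)). With d₁=0.87 and d₂=0.3 this is 0.06525/√(1.1892 × 1.0225) = 0.059. With d₂=0.5 it is 0.097. At retention d=0.435 the values are 0.032 and 0.052.

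Rejection rates of the two-sided 5% test without arm:

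| Retention d | n | Brain d=0 | 0.3 | 0.5 |
|---|---|---|---|---|
| 0.87 | 60 | 5% | 7% | 11% |
| 0.435 | 60 | 5% | 6% | 7% |
| 0.87 | 40 | 5% | 6% | 9% |
| 0.435 | 40 | 5% | 5% | 6% |

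With arm in the model the rate is 5% in every cell. The n=40 rows are an assumption for the MRI measures (gray matter, segregation). Section 6 lets participants enrol without MRI, and the fraction is not given. The fNIRS change does not depend on MRI eligibility, so n=60 is nearer for it, before dropout.

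**4. Opposite-direction shift (sensitivity only; no document predicts it).** Within-arm r=0.355, n=60, retention d=0.87, brain d=0.3 against the hypothesised direction: power is 53% without arm and 80% with it. With no brain shift it is already 73% without arm, so 7 of the 27 points are ordinary precision loss.

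**5. Cost of the extra term.** If arm explains nothing, detectable r becomes tanh(2.802/√56) = 0.358.

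**The case against.** The plan is under-specified here rather than wrong. The unlisted other covariates could include arm, and arm fits their stated purpose. A reader might infer that arm will be left out; the text does not establish that, and every adverse figure above is conditional on it.

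The baseline half describes a possible gain and no defect. The larger gain rests on a pilot of 5 versus 7 people after a single learning session, whereas the trial uses four. At half the pilot effect the gain is about 2 points.

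For change predictors, a reader might infer that the gray matter and fNIRS associations are confounded by tDCS. No hypothesis says that tDCS alters either measure: Hypothesis 2b attributes the change to training, and Hypothesis 3 concerns segregation only. If tDCS does not move the measure, rejection stays at 5%. Rejection above 5% is also an error only if the within-arm association is the target; under a pooled target it detects a real association.

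Two ways of enlarging the figures should be resisted. Extending the assumed brain shift to 0.87 gives 23% at n=60, but that value is the walking-speed effect and has no source for any brain measure. Section 6 allows up to 100 participants, but rates at n=100 should not be applied to MRI measures, because not everyone will be scanned.

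All of this stands, and it limits the size of the point. It does not remove the need to name arm or to state the target for change measures.

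**Conclusion.** The point holds as an inexpensive improvement to a secondary, mechanistic aim. The plan names no arm term in models whose outcome it expects arm to change.

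- **Baseline predictors:** no bias and no error in the 0.355. Precision is forgone only if tDCS affects retention: about 7 points of power at the pilot effect and about 2 at half of it.
- **Change predictors:** the coefficient has no defined target. If tDCS shifts the measure by an assumed d of 0.3 to 0.5, and no within-arm association exists, the unadjusted test rejects in about 6-11% of trials at n=60 and about 5-9% at an assumed n=40.

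These figures assume 1:1 arms, two-sided 5% tests, retention d between 0.435 and 0.87, and a model without arm. The documents do not support reading this as a wrong Aim 2 power calculation, a demonstrated false-positive problem or any threat to the Aim 1 comparison.

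**What to change.** Name randomised arm as a covariate in the Aim 2 models, and list the other covariates. For change measures, add that the arm-adjusted coefficient targets the within-arm association, assuming a common slope in both arms, with an exploratory arm-by-predictor check of that assumption. Report any pooled or mediation analysis separately and label it as such.

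The cost is one degree of freedom per model (detectable r at n=60 moves from 0.355 to 0.358 if arm explains nothing), one more term in the exploratory check, and a few sentences in section 10. No new data are needed.

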Specific Aim 3: Investigate the extent to which tDCS modifies resting state network segregation.

Hypothesis 3: Compared to the sham tDCS group, the active tDCS group will demonstrate improved segregation of resting state networks at post-training relative to baseline.

[figure not shown]
6. Research Plan:

Study Overview

Screening	Baseline	Locomotor Learning	Post (1 Day)	Post (1 Week)	Post (1 Month)
1 Visit	1-2 Visits	4 Visits	1 Visit	1-2 Visits	1 Visit

 • Informed Consent • Cognitive Function • Walking Function 	
 • Obstacle walking with fNIRS • Cognitive Function • MRI: 
 › Structural › Resting state › Task-based (imagined obstacle walking) • Blood Draw 	
 • Active or sham tDCS during: • Obstacle task practice 
 1 - blocked practice 2 - variable practice 3 - combined practice 4 - full task practice 	
 • Obstacle walking with fNIRS 	
 • Obstacle walking with fNIRS • Cognitive Function • MRI: 
 › Structural › Resting state › Task-based (imagined obstacle walking) • Blood Draw 	
 • Obstacle walking with fNIRS • Cognitive Function

Up to one hundred older men and women will be enrolled in the intervention component of this study. An additional 15 participants (estimated) may enroll in the intervention but discontinue participation before completing the protocol. A larger number (up to 400) may participate in screening by telephone and/or onsite, but will fail the screening tests and not proceed to the study intervention. Participants will undergo the following sequence of events:

- *Telephone Screening*: Participants will be screened by telephone to determine if they meet basic enrollment criteria including age and general health status. If patients authorized us to view their medical records, those records may be examined to verify absence of exclusion diagnoses, to obtain complete/accurate medication lists, and to assess whether participants have successfully completed prior MRI scans.

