- *Informed Consent and Onsite Screening Visit*: Participants who pass the phone screen will be invited to participate in on-site screening. Informed consent will be obtained. Mobility function, cognitive function, and health/safety screening will be conducted. This single visit will last approximately 3.5 hours. Qualifying participants will be invited to participate in the full study with or without MRI.
- *Baseline* Participants will undergo a test of walking over obstacles, turning while walking (90 degree turns and 180 degree turns), turning while standing in place (360 degree turn), cognitive function, blood draw, and MRI scans at the UF McKnight Brain Institute (structural, functional, and resting state MRI scans) if MRI screening passed. Baseline assessment will last about 4 hours and may be completed over 1 or 2 visits based on scheduling flexibility of the participant, study personnel, and equipment.
- *Study Intervention Visits*: Participants will attend four intervention sessions in which they will practice a “locomotor learning” task comprised of a 10m walking course with obstacles and transitions between hard and soft floor surfaces. During this task they will receive either active or sham transcranial

The obstacles walking task includes a series of foam obstacles and foam mats. This walking task is used for baseline visits, study intervention visits, and post visits.

direct current stimulation (tDCS) to the frontal portion of the brain. Each visit will last approximately one hour.

- **1-Day Post Assessment:** Participants will undergo a test of walking over obstacles.
- **1-Week Post Assessment:** Participants will undergo a test of walking over obstacles, cognitive function assessment, blood draw, and MRI scans (MRI eligible participants only) at the UF McKnight Brain Institute (structural, functional, and resting state MRI scans). Post assessments will last about 4 hours and may be completed over 1 or 2 visits based on scheduling flexibility of the participant, study personnel, and equipment.
- **Visit 9: 1-Month Post Assessment:** Participants will undergo a test of walking over obstacles, turning tasks, and cognitive function assessment. This visit will last approximately 2 hours.

Telephone Screening

Participants will be screened by telephone to determine if they meet the following criteria:

Inclusion criteria

- Age 65 - 95 years

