- Activities Specific Balance Confidence Scale: 16-item questionnaire that gauges confidence (on a scale of 0-100%) on various balance and walking tasks relevant to household and community ambulation.
- Berg Balance Scale: 14-item assessment of balance task performance to assess balance ability and fall risk.
- Movement-specific Reinvestment Scale: questionnaire that asked about the extent to which a person directs conscious attention to control of movement.
- Montreal Cognitive Assessment (MoCA)
- Trailmaking Test – paper based test where the person must “connect the dots” between numbers or between alternating letters and numbers.
- Sleep quality assessed by the Pittsburgh Sleep Quality Index, which is a questionnaire about sleep-related habits and experiences.

Following the screening visit, study staff will evaluate performance/responses relative to the study enrollment inclusion/exclusion criteria. BMI will be calculated from the height and weight collected. Medical records may be examined to verify absence of exclusion diagnoses, to obtain complete/accurate medication lists, and to assess whether participants have successfully completed prior MRI scans. Individuals who meet all criteria will be invited to enroll in the full study. Participants who screen out of MRI may also be invited to enroll for the study with the MRI portion excluded.

At the discretion of the Principal Investigator, any individual may be deemed ineligible for further participation in this study if there are concerns about the individual's capability to perform study procedures or if it may be unsafe for the volunteer to participate in the study. Furthermore, minor exceptions to the inclusion/exclusion criteria may be permitted at the discretion of the Principal Investigator if those exceptions do not influence participant safety. For example, if a participant walks somewhat faster than the target inclusion criteria for walking speed. This is important to ensure that individuals are not excluded for insignificant reasons and to facilitate meeting enrollment benchmarks.

Baseline Visit(s)

[figure not shown]

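### The Aim 2 detectable correlation of 0.355 needs 60 complete pairs, but section 10 enrols 60 with dropout included, allows for no missing MRI, and is not reconciled with the ceiling of 100 in section 6

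*Combined protocol and SAP*

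**What the plan says.** Section 10 (Statistical analysis and sample size calculations) gives the Aim 2 power statement: "a sample size of 60 with alpha=0.05 and beta=0.20 (i.e., 80% power) will allow us to significantly detect correlations coefficients as small as 0.355". It treats this as the limit of what is worth finding, since below it "there would be little benefit to powering the study to detect smaller values". The Aim 2 outcome is retention one week after training.

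The Aim 1 paragraph of the same section derives a need for 48 participants (24 per group) and then says "we will enroll 60 participants to account for potential dropout and to ensure sufficient statistical power". The 60 is therefore an enrolment figure that already contains the dropout allowance.

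Section 6 (Research Plan, Study Overview) gives other numbers: "Up to one hundred older men and women will be enrolled in the intervention component of this study", and "An additional 15 participants (estimated) may enroll in the intervention but discontinue participation before completing the protocol". Section 10 mentions neither the 100 nor the 15, and section 6 does not mention the 60.

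On MRI, the Study Overview says "Qualifying participants will be invited to participate in the full study with or without MRI", and its 1-week assessment lists "MRI scans (MRI eligible participants only) at the UF McKnight Brain Institute". The detailed text on the onsite screening visit adds: "Participants who screen out of MRI may also be invited to enroll for the study with the MRI portion excluded". Yet the exclusion criteria list MRI contraindications, and the risk section describes known claustrophobia as a bar to participation.

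**The concern.** An enrolled number has been used as an analysed number. Section 10 allows for dropout when it sizes Aim 1, then applies none when it states the power of Aim 2. Anyone lost before the one-week visit contributes no retention value and so no pair.

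The Aim 2 predictors also do not share one sample size. Working memory and fNIRS activity can be measured in everyone. Gray matter volume (Hypothesis 2a), its change with training (2b) and resting network segregation (2c) need MRI, and the change measure needs two scans. If people without MRI are enrolled, these analyses have fewer pairs than the others.

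By the plan's own standard, correlations of 0.355 and above are worth detecting. If the correlation that really has 80% power is higher, a band of such correlations is underpowered, and a null result there could be read too firmly. The unlinked figures of 60 and up to 100 leave the reader unable to tell whether this happens.

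**Working it through.** **Inputs.** From section 10: n = 60, alpha 0.05, power 80%, r = 0.355; 48 needed for Aim 1; 60 enrolled; weakest cited pilot correlation 0.46. From section 6: ceiling of 100, plus an estimated 15 who discontinue. The documents give no share of participants without MRI; 10%, 20% and 30% below are assumptions.

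**Formulas** (Fisher z, two-sided):

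- smallest r with 80% power = tanh[(1.960 + 0.842)/√(n − 3)]
- power at r = Φ[atanh(r)·√(n − 3) − 1.960]

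**The plan's figure.** n = 60: √57 = 7.550; 2.802/7.550 = 0.371; tanh(0.371) = 0.355. Power at 0.355 is 80.0%. The stated figure is reproduced and needs 60 complete pairs. Sidedness is not stated, but a one-sided test would give 0.318, so two-sided is what was used.

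**If 60 are enrolled, measures that need no MRI.**

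- Loss at the rate implied by section 6: 15/115 = 13.0%; 60 × 0.870 = 52.2, so 52 pairs.
- Loss of the whole Aim 1 margin: (60 − 48)/60 = 20%, so 48 pairs. This is the most Aim 1 can tolerate, not a forecast.

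| Pairs | Smallest r, 80% power | Power at r = 0.355 | Power at r = 0.46 |
|---|---|---|---|
| 60 | 0.355 | 80% | 96% |
| 52 | 0.380 | 74% | 94% |
| 48 | 0.395 | 70% | 92% |

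**If 60 are enrolled, MRI measures** (share without MRI assumed):

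| Followed up | Without MRI | Pairs | Smallest r, 80% power | Power at r = 0.355 |
|---|---|---|---|---|
| 52 | 10% | 47 | 0.399 | 69% |
| 52 | 20% | 42 | 0.421 | 64% |
| 52 | 30% | 36 | 0.452 | 57% |
| 48 | 10% | 43 | 0.416 | 65% |
| 48 | 20% | 38 | 0.441 | 59% |
| 48 | 30% | 34 | 0.465 | 54% |

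If nobody is enrolled without MRI, the extra loss is zero and the first table applies to these measures too, provided the scans are usable.

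**If 100 complete.** Smallest r is 0.277 for non-MRI measures, and power at 0.355 is 95.5%. For MRI measures, 100 × 0.60 = 60 pairs remain with 40% lacking MRI, so 0.355 still has 80% power.

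**Sensitivity to the formula.** An exact bivariate normal calculation needs 59 pairs for 0.355, and a fixed-predictor regression needs 57. With 48 pairs they give 71% and 73%, against 70% by Fisher z.

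**The case against.** The strongest reply is that the sentence is correct as written: a sample of 60 does give 0.355. This stands as far as it goes. The formula is sound, and the fault is one of consistency between the number enrolled and the number analysed.

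Second, section 10 gives no dropout rate, and the 13% is borrowed from a passage where those who discontinue come on top of the 100. This also stands. The figure of 52 is illustrative, and the rate may overstate loss by one week because it counts leaving at any point. What remains is that section 10 itself provides for dropout within the 60, so fewer than 60 pairs are to be expected on its own figure.

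Third, 60 and up to 100 do not strictly conflict, since one can be a target and the other a ceiling. That is true, but nothing says so, and the Aim 2 power depends on which is meant.

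Fourth, the MRI shortfall disappears if the listed exclusion for MRI contraindications governs. That is right. Several places in section 6 treat MRI as optional, however, so some MRI loss is the more natural reading.

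Fifth, Aim 2 does not size the trial, and the cited pilot correlations run from 0.46 to 0.57. At 0.46, power is 84% with 38 pairs and 82% with 36; only the most extreme assumed case, 34 pairs, falls just short at 79%. This limits the practical harm. The 0.57 and 0.48, however, concern visuomotor learning rather than obstacle walking, and the 0.46 is for a resting-state connectivity measure, one of those exposed to MRI loss.

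**Conclusion.** The concern holds. The claim of 80% power at r = 0.355 requires 60 complete pairs, and an enrolment of 60 that includes dropout is not expected to supply them. On that enrolment, the correlation with 80% power is about 0.38 to 0.40 for working memory and fNIRS measures, and power at 0.355 is about 70% to 74%. This assumes loss between 13% and 20%. For MRI measures, with an assumed 10% to 30% lacking MRI, the ranges are 0.399 to 0.465 and 54% to 69%.

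All of this is conditional on 60 being the governing figure. If 100 participants complete and at least 60 have MRI, there is no shortfall. The plan does not say which figure applies, so whether the stated power is delivered cannot be settled from the documents. The consequence is moderate: the primary comparison is unaffected, and power at the cited pilot correlations stays high in most of the cases examined. It should be corrected.

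**What to change.** 1. State which enrolment figure governs, and make section 10 (60, dropout included) and section 6 (up to 100, plus an estimated 15 who discontinue) agree.
2. Give the expected number with complete data for each type of Aim 2 predictor, and restate the detectable correlation at that number: one value for working memory and fNIRS, another for MRI measures. If 60 governs, the first is about 0.38 to 0.40 under the loss rates used here; the sponsor should substitute its own expected loss. The second needs the expected share with usable MRI, which the plan does not give.
3. Reconcile the exclusion for MRI contraindications, and the claustrophobia statement in the risk section, with the permission to enrol without MRI. Which rule to keep is for the sponsor; the MRI sample size follows from it.

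The first two changes are wording only and add no participants. The third may alter who can enter. The price is that, if 60 governs, the stated detectable correlation becomes less favourable.
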